Subjects will be asked to consent to have their coded research data placed in the "Mike O'Callaghan Military Medical Center General Research Data Repository" (FWH20180064E), the coded data will be retained for possible use in future research. Subjects may choose either to not allow any further use of their coded data or give consent now for the use of the coded data to be used in future studies. This future research may be in the same area as the original study or it may be for a different kind of study. Any future research using retained data will require a research protocol for the proposed study approved by an Institutional Review Board or other authorized official responsible for protecting human subjects of research.

11.0 Statistical/Data Analysis Plan

11.1 Statistical Considerations:

List the statistical methods to be used to address the primary and secondary objectives, specific aims, and/or research hypotheses. Explain how missing data and outliers will be handled in the analysis. The analysis plan should be consistent with the study objectives. Include any subgroup analyses (e.g., gender or age group). Specify statistical methods and variables for each analysis. Describe how confounding variables will be controlled in the data analysis

The primary outcome and dependent variable will be the degree of toric rotation away from the target axis, and the time point of primary endpoint analysis will be when data for the last repeated measurement at 6 months has been obtained. The main treatment effect is a control group receiving a toric IOL only (Group 1) and a treatment group receiving a toric IOL plus capsular tension ring (Group 2). The statistical null hypotheses is as follows:

H01 — there is no difference in means of the degree of toric rotation away from the target axis between control and treatment groups

Subjects will be a random sample of left or right eyes of male and female patients seen in one Air Force medical treatment facility. The patients are presumed to be randomly selected from the population of patients obtaining similar care at this and other Air Force medical treatment facilities.

The study is organized as a mixed effects, randomized design. Subject (eye) is a random effect, as the patients whose eyes are the subjects of this study are presumed to have been randomly elected to obtain this treatment from the population of patients obtaining similar care at these Air Force medical treatment facilities, and the eyes are randomly assigned to treatment or control groups. Treatment is a fixed effect, as the effect of the intraocular lens and capsular tension ring cannot be generalized to other brands of toric intraocular lens or capsular tension rings.

Reference 5 states eyes treated with a CTR rotated a mean 1.85°(1.72 SD) and eyes without a CTR rotated a mean 4.02°(2.04 SD). The minimum clinically significant difference of toric rotation away from the target axis the researchers wish to detect in this study is 1.85°. Using these parameters, a priori power for a repeated measures n analysis of variance (rANOVA) was assessed using G*Power Version 3.1.9.3. (12). The results indicate 50 subjects (eyes) will have a power of 0.957 at $\alpha = 0.05$ to detect this minimum clinically significant difference between the treatment groups.

Total sample and treatment group means, standard deviations, medians, interquartile ranges (IQR) and ranges will be calculated for interval variables. Frequency distributions will be produced for nominal and ordinal variables. Visual acuity, toric power, intended toric axis, and other variables will be included in the analysis.

The null hypothesis, H01, will be tested by a mixed effects repeated measures analysis of variance (rANOVA) using a general linear model, $y_{ij} = \mu + \alpha_i + \beta_j + \gamma_{ij} + \epsilon_{ij}$, where μ is the main treatment effect, α_i is time of repeated measure, and β_j represents the influence of individual j on his/her repeated observations.

[name], Senior Research Biostatistician Subject Matter Expert for Clinical Research Management under contracts OMNI 0004 3-82 and OMNI 0005 3-126, is the statistical consultant supporting this study. Statistical analysis will be performed with R Version 3.5.1. (13)

11.2 Sample Size:

50 eyes (approximately 25 eyes in each group) -- We are enrolling by number of eyes. If subjects have one eye that meets enrollment criteria, then that eye will be randomized into the treatment or control group. If both eyes meet enrollment criteria, then each eye will be randomized independently.

11.3 Total number of subjects requested (including records and specimens):

50

11.4 If you are recruiting by study arm, please identify the arms of the study and how many subjects will be enrolled in each arm

Randomization: Each eye undergoing cataract surgery will be randomized into a control or treatment group. If both eyes meet enrollment criteria, then each eye will be randomized independently. For patients able to enroll both eyes into the study, potential outcomes could be: a. one eye could be randomized into the control group and one eye could be randomized into the treatment group, b) both eyes could be randomized into the control group, or c) both eyes could be randomized into the treatment group.

- Control group: toric IOL only
- Treatment group: toric IOL plus capsular tension ring

Assignment of the eye to the control or treatment group will be revealed during the cataract surgery at the point of potential capsular tension ring insertion. The surgeon and clinical staff (ophthalmic technicians and nurses) will not know whether the eye is in the treatment/control group until after the cataract has been removed and it is time for potential capsular tension ring placement. The eye will have been previously assigned to the control or treatment group using a random number generator by clinical research personnel, who are not involved in patient care. The group assignment will be documented in an opaque, sealed envelope, which will be present in the operating room at the time of surgery. The envelope will be opened by operating room staff after lens removal, and the surgeon will be informed. If the capsular tension ring is to be implanted, the correct size will be selected and verified, then implanted.

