The lens material can impact the amount of rotation. AcrySof toric intraocular lenses (Alcon Laboratories, Inc.) have been shown to rotate less than Tecnis toric intraocular lenses (Johnson & Johnson Vision), although other brands may rotate even less than both of those.^{1, 10}

Comparison has shown that Precion toric lenses (Ophtec) has slightly less rotation than Tecnis.¹¹ However, no prospective studies have been published to date using capsular tension rings with a newly available lens, the Tecnis Eyhance Toric II lens (Johnson & Johnson Vision). Johnson & Johnson Vision toric intraocular lenses are widely used in the United States due to some of their unique properties, including a square-edge design that reduces posterior capsular opacification, ease of use, and excellent optics. Since more research is needed to determine whether capsular tension rings reduce intraocular lens rotation, and no research has been done with this technique using Johnson & Johnson intraocular lenses, it is worthwhile to study whether capsular tension rings may play a helpful role in reducing rotation in these lenses.

9.3

Objectives/Specific Aims/Research Questions:

Describe the purpose and objective(s) of the study, specific aims, and/or research questions /hypotheses

Null Hypothesis: The use of a capsular tension ring inside the capsular bag will not reduce the degree of rotation of the toric intraocular lens, compared to lenses implanted without a capsular tension ring.

Alternative Hypothesis: The use of a capsular tension ring inside the capsular bag will reduce the degree of rotation of the toric intraocular lens, compared to lenses implanted without a capsular tension ring.

Objective 1: Determine whether the use of a capsular tension ring inside the capsular bag will reduce the degree of rotation of the toric intraocular lens, compared to lenses implanted without a capsular tension ring.

9.4 Study Design:

Describe study design in one to two sentences (e.g., prospective, use of existing records/data /specimens, observational, cross-sectional, interventional, randomized, placebo-controlled, cohort, etc.). Specify the phase – Phase I, II, III, or IV – for FDA-regulated investigational drug research

To investigate whether implantation of a capsular tension ring device will affect the degree of rotation of an implanted toric intraocular lens following cataract surgery.

9.5 Target Population:

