For example, if only one eye meets criteria (for example, one eye has a surgical plan that includes a toric IOL and the other eye doesn't), then only one eye will be enrolled in the study. However, if the fellow eye also meets criteria, then both eyes will be enrolled in the study.

Lens Selection: The patients will undergo standard of care preoperative measurements and planning. The surgeon will evaluate preoperative measurements and use lens calculations, as well as a discussion with the patient, to identify whether a toric lens will be used and to determine the IOL power, cylinder, and target axis (standard of care). Preoperative measurements will be taken using IOL-Master 700, with the addition of the Pentacam and automatic keratometry as needed (standard of care). The toric lens used will be either Tecnis toric II or the Tecnis Eyhance Toric II intraocular lens (Johnson & Johnson Vision). The surgeon, in conjunction with a thorough discussion with the patient, will decide whether to use the Tecnis Toric II or the Tecnis Eyhance Toric II lens based on the patient's pre-existing ocular conditions (prior corneal refractive surgery, irregular corneal astigmatism, severe corneal dystrophy, macular disease, optic atrophy, etc.), refractive goals, lens status of the other eye, and other preoperative factors. All lenses will be used on label (standard of care).

Capsular Tension Ring Selection: The capsular tension rings used in this study will be the MORCHER® EYEJET® CTR Types 14, 14A, and 14C. MORCHER® EYEJET® CTR is a preloaded single-use injector plus capsular tension ring. It is available in two variations: for implantation clockwise (right), and for implantation counterclockwise (left). The clockwise (right) variation will be used in this study.

As recommended by the MORCHER® Instructions for Use, the anatomy of the eye, specifically the bulbous (axial) length, will be taken into account in the selection of the proper CTR size. CTR model 14C is 13.0mm in overall diameter and has a compressed diameter of 11 mm. It is intended for implantation in eyes with axial length of 24-28 mm. CTR model 14 is 12.3 mm in overall diameter and compresses to 10.0 mm. It is intended for implantation in eyes with axial length less than 28 mm. CTR model 14A is 14.5 mm in overall diameter and compresses to 12.0 mm. It is intended for implantation in eyes with bulbous length greater than 28 mm.

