Measurements taken preoperatively on the IOL Master 700 will be used to determine the axial length of the study eye. If the axial length cannot be determined using the IOL Master 700, then the axial length measured by non-contact immersion A-scan will be used. For this study, the following selection protocol will be used (standard of care):

- Axial length > 28.0 mm: CTR model 14A
- Axial length 24.0-28.0 mm: CTR model 14C
- Axial length < 24.0 mm: CTR model 14

Labeling: The outer box of the capsular tension rings used in this study will be clearly labeled with the following statement: "CAUTION—Investigational Use. Limited by Federal (or United States) law to investigational use." This is in accordance with FDA-approved labeling procedures. In addition, the capsular tension ring selected for each eye will be packaged with the chosen intraocular lenses and labeled with the patient's name to prevent another patient receiving the device accidentally.

Randomization: Each eye undergoing cataract surgery will be randomized into a control or treatment group. If both eyes meet enrollment criteria, then each eye will be randomized independently. For patients able to enroll both eyes into the study, potential outcomes could be: a. one eye could be randomized into the control group and one eye could be randomized into the treatment group, b) both eyes could be randomized into the control group, or c) both eyes could be randomized into the treatment group.

- Control group: toric IOL only
- Treatment group: toric IOL plus capsular tension ring

Assignment of the eye to the control or treatment group will be revealed during the cataract surgery at the point of potential capsular tension ring insertion. The surgeon and clinical staff (ophthalmic technicians and nurses) will not know whether the eye is in the treatment/control group until after the cataract has been removed and it is time for potential capsular tension ring placement. The eye will have been previously assigned to the control or treatment group using a random number generator by clinical research personnel, who are not involved in patient care. The group assignment will be documented in an opaque, sealed envelope, which will be present in the operating room at the time of surgery. The envelope will be opened by operating room staff after lens removal, and the surgeon will be informed. If the capsular tension ring is to be implanted, the correct size will be selected and verified, then implanted.

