It was recommended by the reviewers during the FDA Investigative Device Exemption (IDE) approval process that the assignment to the control or treatment group should be revealed as late as possible (that is, during surgery immediately before the capsular tension ring would need to be inserted). This is to prevent the surgeon's technique during the first part of the cataract surgery from influencing the outcome. For example, there is a point during the surgery where the surgeon makes a round, even opening in the lens capsule called a capsulorrhexis. The size and contour of the capsulorrhexis have been thought to influence lens position and rotation later on, and therefore would affect the results of the study. It is important that the surgeon make a round, even capsulorrhexis opening without being influenced by whether the eye is assigned to the control or treatment group. It may also be helpful to know that the decision to implant a capsular tension ring for its usual indication (weakened or missing zonules) is often made during surgery, when zonular weakness is identified. The method of our study therefore mimics a common use of capsular tension rings.

Surgery: Patients will undergo manual phacoemulsification small-incision cataract surgery. The preoperative axis for toric placement will be marked while seated upright in the preoperative holding area. Standard of care phacoemulsification cataract surgery through a manual clear corneal incision will then take place. For the treatment group, after completing removal of the lens and cortex, the capsular bag will be inflated with cohesive viscoelastic and the capsular tension ring inserted. The intraocular lens will be placed in the capsular bag. The viscoelastic

material will be removed, with attention given to careful removal behind the IOL. The lens will be rotated to the final target axis. Care will be taken to ensure the final rotation occurs in the direction of haptic orientation (clockwise). The techniques used in the surgery will be standard of care.

If both eyes are enrolled in the study, there will be a minimum time of 7 days between surgery dates.

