If both eyes are enrolled in the study, then the visits on post-operative day #1 and post-operative week #1 will involve dilation and slit lamp photography only on the eye which has most recently had surgery. The rest of the post-operative visits (month #1, month #3, month #6) will be combined visits with dilation and slit lamp photography for both enrolled eyes. Please see the description of the study visits, below.

During the pre-operative anesthesia visit, which is standard of care for this surgery, subjects will receive either a standard of care pregnancy test or be asked about their ability to become pregnant and/or lactating. If they are pregnant or lactating, they will not be eligible for this research study.

Post-Operative Day #1 Visit:

- The eye enrolled in the study will be dilated and slit lamp photography taken using retro-illumination. A standard of care postoperative evaluation will be performed, including checking visual acuity, eye pressure, slit lamp exam, and the rest of the postoperative evaluation.
- Dilation and slit lamp photography will be performed only on the post-operative day #1 eye.

Post-Operative Week #1 Visit (5-10 days after surgery):

- The eye enrolled in the study will be dilated and slit lamp photography taken using retro-illumination. A standard of care postoperative evaluation will be performed, including checking visual acuity, eye pressure, slit lamp exam, and the rest of the postoperative evaluation.
- Dilation and slit lamp photography will be performed only on the post-operative week #1 eye.

Post-Operative Month #1 Visit (4-6 weeks after surgery):

- The eye(s) enrolled in the study will be dilated and slit lamp photography taken using retro-illumination. A standard of care postoperative evaluation will be performed, including checking visual acuity, eye pressure, slit lamp exam, and the rest of the postoperative evaluation.
- If both eyes are enrolled, dilation and slit lamp photography will be performed on both eyes.

Post-Operative Month #3 Visit (75-120 days after surgery):

- The eye(s) enrolled in the study will be dilated and slit lamp photography taken using retro-illumination. A standard of care postoperative evaluation will be performed, including checking visual acuity, eye pressure, slit lamp exam, and the rest of the postoperative evaluation.
- If both eyes are enrolled, dilation and slit lamp photography will be performed on both eyes.

Post-Operative Month #6 Visit (165-210 days after surgery):

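### The primary outcome, deviation from the target axis, mixes placement error with lens rotation; the planned analysis does not separate them, which can dilute the ring's effect

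*Combined protocol and SAP*

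**What the plan says.** - **Objective (9.3).** "Determine whether the use of a capsular tension ring inside the capsular bag will reduce the degree of rotation of the toric intraocular lens", compared with lenses implanted without one. The background in 9.2 describes the problem as lenses moving out of position after the operation.
- **Outcome and null hypothesis (11.1, repeated in 11.6).** "The primary outcome and dependent variable will be the degree of toric rotation away from the target axis". The null is that "there is no difference in means of the degree of toric rotation away from the target axis between control and treatment groups".
- **Target axis (10.1, Lens Selection).** It comes from preoperative measurements and lens calculations, used "to determine the IOL power, cylinder, and target axis". The axis is marked in the holding area before surgery.
- **Reveal and alignment (10.1, Randomization and Surgery).** "The envelope will be opened by operating room staff after lens removal, and the surgeon will be informed". The ring step, lens insertion and viscoelastic removal follow, and then "The lens will be rotated to the final target axis". The protocol does not ask for the achieved axis to be recorded at the end of surgery.
- **First image (10.1, day-1 visit).** "The eye enrolled in the study will be dilated and slit lamp photography taken using retro-illumination". Photographs follow at week 1 and months 1, 3 and 6. Masked evaluators read the lens axis against the horizontal.
- **Model (11.1, 11.6).** Terms for treatment, time and individual. There is no day-1 reference and no named treatment-by-time test.

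**The concern.** The question is about movement of the lens, but the outcome is distance from a plan made before surgery. An eye can be several degrees off target at month 6 because the lens turned, because it was marked or set down off target, or both. Final alignment, which directly sets this distance, is done by a surgeon who knows the arm. Masked reading of the photographs does not cover that step.

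Two things are at stake. Placement error unrelated to the ring adds noise and shrinks a difference in absolute deviations, so a null result might mean only that placement error hid a real effect on rotation. And if alignment accuracy differed between arms, that difference would be read as an effect on rotation.

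**Working it through.** **1. Inputs.** From 11.1: with ring, mean 1.85 (SD 1.72) degrees; without ring, mean 4.02 (SD 2.04); difference to detect 1.85; alpha 0.05; stated power 0.957. From 11.2: 50 eyes, about 25 per arm. The documents give no placement error, so its SD, τ, is an assumption, varied from 0 to 3 degrees.

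**2. The plan's own figure.** Pooled SD = √((1.72² + 2.04²)/2) = 1.887, so d = 1.85/1.887 = 0.980 and f = 0.490. For the between-group test in a repeated measures ANOVA, λ = f²·N·m/(1 + (m − 1)ρ). With N = 50, m = 5 visits and ρ = 0.80, λ = 14.3 and power is 0.960; ρ of about 0.817 gives 0.957. The stated power is therefore reachable, although 11.1 gives neither m nor ρ. A two-sided t-test at a single visit gives 0.925. Either way, the cited SDs are carried over with no allowance for placement error beyond what they already contain.

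**3. Dilution when placement error is equal by arm.** Let R be rotation and E ~ Normal(0, τ²) the placement error, independent of R. The outcome is |R + E|. Take |R| as gamma with mean m and SD s: 4.02 and 2.04 for control; 4.02 − 1.85 = 2.17 and 1.72 for ring.

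- Mean of |R + E| = average over |R| = r of τ√(2/π)·exp(−r²/2τ²) + r[1 − 2Φ(−r/τ)].
- SD = √(m² + s² + τ² − mean²).
- Noncentrality = difference/(pooled SD × √(2/25)), with 48 df, two-sided 0.05.

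For τ = 2:
- Control: mean 4.163; SD = √(16.160 + 4.162 + 4 − 17.331) = 2.644.
- Ring: mean 2.688; SD = √(4.709 + 2.958 + 4 − 7.225) = 2.108.
- Difference 1.476; pooled SD 2.391; noncentrality 1.476/(2.391 × 0.2828) = 2.18; power 0.57.

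| Assumed τ (degrees) | Control mean (SD) | Ring mean (SD) | Difference | Power |
|---|---|---|---|---|
| 0 | 4.02 (2.04) | 2.17 (1.72) | 1.85 | 0.92 |
| 1 | 4.03 (2.25) | 2.30 (1.84) | 1.74 | 0.83 |
| 2 | 4.16 (2.64) | 2.69 (2.11) | 1.48 | 0.57 |
| 3 | 4.46 (3.07) | 3.23 (2.49) | 1.23 | 0.33 |

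These are single-visit t-test figures. Repeated visits do not average the placement part away, because an offset made at surgery is carried to every later visit. The individual term does not remove it from the comparison either, since treatment varies between eyes.

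**4. Error rate.** If the ring has no effect on rotation and τ is the same in both arms, |R + E| has the same distribution in both arms, and the rejection rate stays at 0.05.

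**5. Unequal placement error, no effect on rotation (hypothetical).** The result depends strongly on the assumed rotation in both arms:

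| Mean rotation, both arms | τ control / ring | False difference | Rejection rate |
|---|---|---|---|
| 4.02 | 3 / 2 | 0.30 | 0.065 |
| 4.02 | 3 / 1 | 0.43 | 0.085 |
| 2.17 | 3 / 2 | 0.55 | 0.13 |
| 2.17 | 3 / 1 | 0.94 | 0.32 |

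**The case against.** The outcome is defensible. Section 9.2 ties the loss of astigmatic correction to each degree away from the target. Sections 11.1 and 11.6 use that definition consistently for the outcome, the null hypothesis and the detectable difference. It is what the patient experiences, and it captures rotation in the first 24 hours, which a day-1 baseline would miss. This stands, and is why deviation from target should remain primary.

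A reader might infer that the trial cannot tell whether the ring reduces rotation. The documents do not support that. Eyes are randomised, both arms are aligned to a target chosen in the same way, and the readers are masked. With equal placement error, a significant result still points to rotation, and the price is power. The scheduled photographs also allow rotation after day 1 to be isolated, although the plan names no such analysis.

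A reader might also infer that the unmasked alignment biases the result. Marking is done before the reveal, so it should not differ by arm. Only the final alignment is exposed, and nothing in the documents suggests that it is more accurate in one arm. A surgeon cannot be masked to inserting a ring, so a late reveal with masked reading is close to the practical limit.

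The size is also uncertain. The documents say only that eyes in the cited study rotated by those amounts. If that study measured from the target axis, its SDs already contain some placement error, and the table in step 3 overstates the loss. The plan does not say whether deviation is signed or absolute; the calculation assumes absolute.

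**Conclusion.** The concern holds in a limited form. Objective and outcome do not match, and the analysis as planned does not separate placement error from rotation, although masked photographs that would partly do so are already scheduled. The likely cost is dilution. For assumed placement SDs of 1 to 3 degrees, power for the planned 1.85-degree difference falls from about 0.92 to between 0.83 and 0.33. This rests on four assumptions: the cited figures are pure rotation, absolute deviation is analysed, placement error is Normal and independent of rotation, and it is equal by arm. The 5% error rate is not threatened under equal placement error. Bias is something the design permits, not something the documents show. The change is worth making because it lets the trial address its own question at almost no cost.

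**What to change.** In 11.1 and 11.6:

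1. Keep deviation from the target axis as the primary outcome, describe it as misalignment from target, and state that the absolute value is analysed.
2. Prespecify as a secondary outcome the absolute change in axis from each eye's day-1 photograph to its month-6 photograph, read by the same masked evaluators. Compare the arms with an estimate and 95% CI.
3. Tabulate day-1 deviation from target by arm, labelled as placement error plus first-day rotation. It should not be labelled placement error alone, because any early benefit of the ring would then be credited to placement.
4. Interpret any claim about rotation using both results. Do not require merely that they point the same way: with no effect after day 1, that is met about half the time, and if the ring acts mainly before day 1 it could block a correct conclusion.

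The cost is plan wording, one derived variable and one table, with no new visit, image or patient. The limits should be stated: change from day 1 misses rotation in the first 24 hours and carries two reading errors, so it complements the primary outcome and does not replace it. An axis recorded at the end of surgery would separate the parts more fully, but it would add a procedure.
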